This study will enroll up to 30 patients in order to evaluate 20 subjects. Infants will be screened for eligibility by the research team using routinely available clinical data from the electronic health record. Informed consent will be obtained from parents or guardians approached within the HUP ICN, PAH ICN, or the CHOP N/IICU during the eligibility window as described below. The diagram depicted in Figure 4 summarizes expected enrollment in consideration of our eligibility criteria and additional barriers to successful recruitment and study application. This estimate suggests a 10-month window of active enrollment will be required to meet our recruitment goals, making our one-year recruitment goal feasible. Aim 1 guides sample size considerations. Using a paired test of correlated means, a sample size of 20 evaluated infants will provide 80% power to detect an overall average percent change of 10% from baseline, assuming a 15% standard deviation of the difference and a two-sided alpha level of 0.05.

Key inclusion criteria

I1. 27-35 weeks corrected gestational age (CGA) by best obstetric estimate, determined by the clinical obstetric team during antepartum admission and chronologic age, measured from date of birth I2. Chronologic age greater than 24 hours, measured from time of birth. I3. On CPAP support between 4-8 cm H₂O for greater than 24 hours, as document on the bedside infant flow sheet. I4. Supplemental oxygen requirement, with a fraction of inspired oxygen (FiO₂) 0.25 for at least 2 consecutive hours, as documented on the bedside infant flow sheet. (Infants without an oxygenation requirement are unlikely to have significant V/Q mismatch. Further, FiO₂ titrations (see Procedures) are required to apply the non-invasive technique, resulting in limited applicability to infants with little or no supplemental oxygen requirement).

Key exclusion criteria

E1. Congenital anomalies, as determined by the clinical supervising physician. E2. Current or prior air leak syndrome, as determined by the clinical supervising physician.

Vulnerable Populations

Children Form

Pregnant women (if the study procedures may affect the condition of the pregnant woman or fetus) Form

Fetuses and/or Neonates Form

Prisoners Form

Other

None of the above populations are included in the research study

The following documents are currently attached to this item:

There are no documents attached for this item.

Populations vulnerable to undue influence or coercion

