
No active consideration of endotracheal intubation; as determined by the clinical Attending of record. 2. No hemodynamic instability, defined as a baseline heart rate less than 100 beats per minute (bpm) or greater than 180 bpm; or a mean arterial blood pressure of less than 30 millimeters of mercury (mm Hg). 3. No supplemental FiO₂ requirement greater than 0.45. 4. No capillary/arterial partial pressure of carbon dioxide greater than 65 mm Hg on last blood gas analysis, unless performed more than 6 hours prior. 5. No more than 6 apnea/bradycardia/desaturation events requiring tactile stimulation or more than 1 requiring positive pressure bag ventilation in the preceding 6 hours. Initiation of the study protocol will be deferred until these criteria are met. Figure 3 depicts the study protocol as applied in one hypothetical subject. Of note, the protocol will vary between subjects with respect to the direction and extent of CPAP level changes, as determined by the absence or presence of a response at each step-wise CPAP level change. This is described in detail below. Subjects will undergo the study interventions in their routine clinical environment. The clinically selected CPAP interface and pressure source will be maintained. A study pulse-oximeter, with low motion artifact and a short averaging time, will be placed on a post-ductal limb and used for SpO₂ measurements. V/Q will first be measured on two separate occasions 30 minutes apart at baseline CPAP, set by the clinical team. The repeat baseline measures will allow an estimate of the stability of V/Q as a function of time (further discussed in Confounding under Analysis Plan). To measure V/Q mismatch, gradual changes in delivered FiO₂, followed by SpO₂ measurement, will be applied to obtain three FiO₂/SpO₂ pairs, one each for SpO₂ values in the ranges of 85-87%, 89-91% and 93-95%. To obtain each SpO₂ range, FiO₂ will be titrated gradually until SpO₂ falls within the desired values. After 60 seconds of stabilization at the identified FiO₂ value, SpO₂ will be recorded every 30 seconds for 2 minutes if an adequate signal waveform is present, providing up to four SpO₂ values. These values will be averaged to calculate the SpO₂ value used for the FiO₂/SpO₂ pair, acknowledging the inherent instability of pulse-oximeter values over time in premature infants. A computer software program will immediately calculate V/Q from the identified FiO₂/SpO₂ pairs at the bedside. Next, CPAP will be increased by +1 cm H₂O. A period of 15 minutes will elapse to allow equilibration of lung volumes in response to the CPAP level change (24). V/Q calculations as described above will be repeated. A positive response will be defined as an improvement in V/Q at the new pressure level of 5% relative to the preceding CPAP level. Responders will undergo subsequent stepwise +1 cm H₂O increases up to +3 cm H₂O from baseline or 8 cm H₂O; whichever is less. Infants not responding to the initial +1 cm H₂O increase will return to baseline CPAP for 15 minutes and then be assessed at -1 cm H₂O from baseline. Infants responding at this lower CPAP level will undergo an additional decrease to -2 cm H₂O from baseline or 3 cm H₂O; whichever is greater. The allowed range of -2 to +3 cm H₂O reflects our institutional practice of typically setting a baseline CPAP level of 5 or 6 cm H₂O and a CPAP pressure range of 4 to 8 cm H₂O used in international trials. Best CPAP will be defined as the lowest (and last) CPAP level at which a positive response, as defined above, is measured. The baseline CPAP level will be defined as best for those infants not responding to either +1 or -1 cm H₂O CPAP level changes, with a corresponding V/Q improvement of zero. Upon completion of the study protocol, infants will be returned to their baseline CPAP level. The study protocol will typically require between 60 and 120 minutes. Throughout the study, a set of pre-defined stopping criteria will be monitored to ensure subject tolerance of the study procedures. These criteria are designed to be conservative safety measures and will result in study termination and provision of supportive care, as needed. Patient Safety Considerations: Extensive patient safety considerations minimizing the risks associated with implementation of this phase II design research protocol have been incorporated: 1. Many of the key eligibility (inclusions and exclusion) criteria reflect the deliberate selection of a premature infant population that is inherently less vulnerable and at lower risk of common morbidities of prematurity and less likely to suffer any adverse outcomes from implementation of the study procedures. a) I1. Corrected gestational age 27-35 weeks (GA): this selects a study population in which respiratory distress syndrome is common and CPAP is frequently used, while avoiding less mature infants with a CGA less than 27 weeks who are more prone to physiologic instability. We exclude this population in consideration of safety for this phase II study despite a high risk of CPAP failure and a potential for benefit from our long-term research goals of establishing methods to prevent CPAP failure. b) I2. Chronologic age of greater than 24 hours. This avoids study of infants during the first 24 hours of life when they may be more prone to physiologic instability. c) I3. On continuous CPAP support for greater than 24 hours. This prioritizes safety by restricting study to subjects demonstrating stability on CPAP therapy, in contrast to infants newly transitioned to CPAP without a period of demonstrated tolerance. d) I4. Supplemental oxygen requirement, with a fraction of inspired oxygen (FiO₂) 0.25 for at least 2 consecutive hours. This ensures that CPAP level changes are only performed in infants requiring supplemental oxygenation, suggesting V/Q mismatch and/or shunt from atelectasis. These subjects would plausibly benefit from carefully monitored changes in continuous distending airway pressure to counteract the pathophysiology resulting in the oxygen need. This criteria avoids CPAP

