
The following documents are currently attached to this item:

There are no documents attached for this item.

Deception

Does your project use deception?

No

International Research

Are you conducting research outside of the United States?

No

Analysis Plan

Results will be summarized using basic descriptive statistics. For Aim 1, a paired t-test for parametric results or a Wilcoxon signed-rank test for non-parametric results will be used to test our hypothesis that V/Q mismatch will improve at best CPAP level compared to baseline. For Aim 2, we will calculate the proportion of subjects in which best CPAP level is identified above the baseline pressure level to assess our hypothesis that this occurs in greater than 50% but less than 80% of subjects. Further, best CPAP for the cohort will be summarized as mean and standard deviation (if parametric) or median and interquartile range (if non-parametric). No formal statistical testing of significance will be performed for this second descriptive Aim. The change in V/Q over the two baseline periods, as well as the change in heart rate and blood pressure between baseline and best CPAP levels will be tested using the statistical approach as Aim 1. We predict the null hypothesis of no significant difference for these comparisons. Should a significant change in V/Q be identified between baseline periods, we will perform an additional analysis comparing the change in V/Q between baseline periods to the change in V/Q between baseline and best CPAP level to account for the independent impact of time on V/Q

mismatch. Confounding: key elements of our study design limit confounding for Aim 1, to measure the responsiveness of V/Q mismatch to a strategy of individualized CPAP level selection. The use of a pre-post within-patient analysis limits confounding from variation in between-patient characteristics. A remaining important source of confounding is the possibility that V/Q simply improves over time irrespective of CPAP pressure changes. We account for this by measuring V/Q on two separate occasions 30 minutes apart at baseline CPAP in the study protocol, facilitating an assessment of the stability of V/Q over time.

The following documents are currently attached to this item:

There are no documents attached for this item.

Data confidentiality

- Paper-based records will be kept in a secure location and only be accessible to personnel involved in the study.**

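### Aim 2: testing +1 first against a single-reading 5% bar lets noise inflate the above-baseline proportion, and the repeat baseline that could show this is not used for it

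*Combined protocol and SAP*

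**What the plan says.** All references are to the combined protocol and SAP.

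- **Procedures, Study Protocol.** V/Q is measured twice at baseline CPAP, 30 minutes apart. Then "Next, CPAP will be increased by +1" cm H₂O. The response rule is: "A positive response will be defined as an improvement in V/Q at the new pressure level of 5% relative to the preceding CPAP level". Each comparison sets one V/Q reading against one other.
- **Same section.** Only "Infants not responding to the initial +1" cm H₂O increase go back to baseline and are assessed at -1. The text does not say whether V/Q is re-measured after that return. The third label is given by default: "The baseline CPAP level will be defined as best for those infants not responding to either +1 or -1" cm H₂O.
- **Analysis Plan, Aim 2.** "we will calculate the proportion of subjects in which best CPAP level is identified above the baseline pressure level", to be judged descriptively against a range of 50% to 80%. No significance test is planned.
- **Overall objectives, Aim 2.** A result in that range is to be read as most, but not all, infants benefiting from higher pressure.
- **Use of the repeat baseline.** Procedures says: "The repeat baseline measures will allow an estimate of the stability of V/Q as a function of time". The Analysis Plan tests the mean change between the two baselines and, only if that is significant, compares it with the change in V/Q from baseline to best CPAP. Nothing applies the 5% rule to the baseline pair, and nothing links that pair to the Aim 2 proportion.

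**The concern.** A one-reading threshold is crossed by chance whenever the noise in the difference is not small against 5%. Each V/Q value is fitted to three FiO₂/SpO₂ pairs, and Procedures itself acknowledges that pulse-oximeter readings are unstable in these infants.

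The order of testing makes the chance crossings lopsided. All infants are exposed to a false crossing at +1. Only those left over are exposed to one at -1, and an infant who crosses at +1 by chance never has the lower level tried.

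The planned check on the baselines looks for a mean shift. Noise without drift has a mean change of zero, so it passes that check and still creates false responders.

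What is at stake is the Aim 2 conclusion. Some of the infants counted as benefiting from higher pressure may only have had a favourable second reading, and the report as planned gives no way to tell how many.

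**Working it through.** **1. The plan's own figure.** The claim in Accrual is: "a sample size of 20 evaluated infants will provide 80% power to detect an overall average percent change of 10% from baseline". Its inputs are an SD of 15% and a two-sided 5% test. Paired t-test power from the noncentral t, with n = 20 and noncentrality (10/15)·√20 = 2.98, is 80.7%. The stated 80% is reproduced. The 15% is the SD of the baseline-to-best difference. It may include true variation in response, so it is at most an upper guide to noise. The documents give no V/Q repeatability SD, so a range is used.

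**2. Chance crossing at +1.** With no CPAP effect and no drift, P(label above) ≈ 1 − Φ(5/SD), where SD is that of the difference between two readings:

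- SD 3%: 1 − Φ(1.67) = 4.8%
- SD 5%: 1 − Φ(1.00) = 15.9%
- SD 10%: 1 − Φ(0.50) = 30.9%
- SD 15%: 1 − Φ(0.33) = 36.9%

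**3. The full step rule.** Simulation with 1,000,000 infants per setting, independent normal errors and the second baseline as reference. Results differ slightly from step 2 because the percentage is taken of a noisy reading.

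| SD of difference | Above | Below, baseline not re-measured | Below, re-measured | Sham: second baseline ≥5% better than first |
|---|---|---|---|---|
| 3% | 4% | 3% | 4% | 4% |
| 5% | 15% | 10% | 13% | 15% |
| 10% | 30% | 15% | 21% | 30% |
| 15% | 37% | 16% | 23% | 37% |

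For SD 5% to 15%, that is 20 × 0.153 ≈ 3 to 20 × 0.367 ≈ 7 infants labelled above baseline by noise. The tilt upward remains if baseline is re-measured, but is smaller. With no effect, the sham share matches the false above-baseline share.

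**4. Can noise alone pass 50%?** The binomial P(at least 11 of 20) at the rates in step 3 is about 0 (SD 5%), 2% (SD 10%) and 7% (SD 15%). Rarely.

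**5. Noise plus a true minority.** With true share t, false rate f (step 2) and every true responder detected, the apparent share is t + (1 − t)f. Setting this to 50% gives t = (0.5 − f)/(1 − f):

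- SD 5%: (0.5 − 0.159)/0.841 = 41%
- SD 10%: (0.5 − 0.309)/0.691 = 28%
- SD 15%: (0.5 − 0.369)/0.631 = 21%

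Full detection is the favourable case for inflation. If some true responders are missed, a larger t is needed.

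**6. Is the excess over sham a corrected estimate?** No. Under the same model, the excess is t + (1 − t)f − f = t(1 − f), which is below t whenever t > 0. Simulation of the +1 step with t = 60% and a true 10% improvement in responders gives:

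| SD of difference | Raw proportion | Excess over sham |
|---|---|---|
| 5% | 57% | 42% |
| 10% | 54% | 24% |
| 15% | 53% | 16% |

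**7. Precision at 20 infants.** The two steps share the second baseline, so the crossings are negatively correlated (ρ about −0.15 at SD 5%, −0.31 at SD 15%). SE = √[2p(1 − p)(1 − ρ)/20]:

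- SD 5%: √(2 × 0.153 × 0.847 × 1.154/20) = 12 points
- SD 15%: √(2 × 0.367 × 0.633 × 1.305/20) = 17 points

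With true responders present it reaches about 18 points.

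**The case against.** The strongest reply has four parts.

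- **The size rests on an SD that the documents do not give.** This stands. Procedures reduces noise by averaging up to four SpO₂ values per pair after a stabilisation minute. At SD 3% the false share is about 4% and the matter is small. The 15% from Accrual should not be taken as the noise SD.
- **Aim 2 is exploratory and untested.** Also true, so no type I error is at issue. But Overall objectives attaches a substantive reading to the proportion, and that reading depends on how often the 5% bar is crossed with no change in CPAP.
- **The repeat baseline is already analysed.** Only in part. The planned test addresses drift for Aim 1, not chance crossings for Aim 2.
- **Subtracting the sham share would do more harm than good.** A reader might infer that the excess over sham is the bias-free share of responders and should be set against 50% to 80%. Step 6 shows otherwise. With a true share of 60% and a 10% improvement, the raw figure is nearer the truth at every SD tried, and the excess would deny a true majority. The sham share measures the bias only when nobody truly responds. It is a benchmark, not a correction.

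**Conclusion.** The point holds in a limited form. By construction, the step order and the single-reading bar inflate the raw Aim 2 proportion when few infants truly respond, and the plan does not use the data that would show by how much. With no CPAP effect the share labelled above baseline is about 4% at a noise SD of 3% and 15% to 37% for SD 5% to 15%, the last being an upper figure. These figures assume independent, roughly normal reading errors and no drift.

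A reader might go further and infer that noise alone would confirm the hypothesis of more than 50%. The calculations do not support that: it would happen in about 7% of trials at SD 15% and less often below. What can happen is that a true minority is reported as a majority, with a true share of 21% to 41% showing as 50% if all true responders are detected. Nor do the figures show that the inflation persists at any true share: at 60% true responders with a 10% improvement, the raw proportion is slightly low. This is a matter of interpretation for a descriptive aim, worth correcting because the remedy is nearly free.

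**What to change.** In the Analysis Plan, under Aim 2:

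1. Apply the same 5% rule to the change from first to second baseline, and report the share of infants who cross it as the sham share.
2. Report the repeatability SD of V/Q from the two baselines.
3. Show both beside the above-baseline proportion, with the paired difference and its 95% confidence interval from a method for paired proportions.
4. Keep the raw proportion as the descriptive Aim 2 figure. State that the difference is not an estimate of the share of responders and is not to be compared with 50% to 80%.
5. Make the statement in Overall objectives that infants benefit from higher pressure only if the above-baseline share clearly exceeds the sham share.
6. State whether V/Q is re-measured after the return to baseline, since the share labelled below depends on it.

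The cost is one table row and a few sentences, from data already collected. No CPAP step, order or procedure changes. The drawback is precision: an SE of 12 to 18 points gives an interval of roughly ±24 to ±35 points (1.96 × SE). If noise is large, 20 infants may not separate the two shares, and the report should say so. If repeatability is good, the same row strengthens the Aim 2 result.

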
level changes in infants on CPAP but not requiring supplemental oxygen as they are less likely to benefit from changes in pressure level. e) E2. Exclusion of infants with current or prior air leak syndrome. This avoids study in infants with suggestion of a pathophysiology that could worsen with increased CPAP levels. 2. To further avoid study in infants with physiologic instability, the following criteria will be met prior to initiation of the study procedures; with deferral of the study until they are met: a. No active consideration of endotracheal intubation; as determined by the clinical Attending of record. b. No hemodynamic instability, defined as a baseline heart rate less than 100 beats per minute (bpm) or greater than 180 bpm; or a mean arterial blood pressure of less than 30 millimeters of mercury (mm Hg). c. No supplemental FiO₂ requirement greater than 0.45. d. No capillary/arterial partial pressure of carbon dioxide greater than 65 mm Hg on last blood gas analysis, unless performed more than 6 hours prior. e. No more than 6 apnea/bradycardia/desaturation events requiring tactile stimulation or more than 1 requiring positive pressure bag ventilation in the preceding 6 hours. 3. Stepwise changes in CPAP level, with assessment after each CPAP level change and restriction of further pressure changes to instances in which there is a response suggestive of improving physiology - defined as greater than a 5% improvement of baseline V/Q mismatch. Infants who are at inadequate lung volumes at baseline CPAP are likely to show benefit with higher pressure levels, while infants with adequate lung volumes at baseline CPAP are unlikely to show any physiologic benefit at higher pressure levels. Similarly, infants with over distended lung volumes at baseline may benefit from lower pressure levels, while infants with adequate lung volumes at baseline CPAP are unlikely to show benefit with lower pressure levels. This key element of study procedures will protect against the risk of over-distension or loss of lung volumes secondary to the study procedures. 4. Stopping Criteria. The following "stopping criteria" will be monitored in each subject throughout the study procedures and will result in study termination, provision of supportive care and a return to baseline settings when appropriate: a) a drop in mean arterial pressure to a mmHg value less than 30 mm Hg and in excess of 10% from the baseline value, or in excess of 20% of baseline value. b) an increase in heart rate to greater than 190 bpm and in excess of 10% from the baseline value or in excess of 20% of the baseline value. c) with an adequate pulse waveform, a sustained drop in SpO₂ to less than 80% for greater than one minute or a drop in SpO₂, to less than 75% for greater than 30 seconds or less than 45% for any duration of time. d) a two-fold increase in the hourly frequency of cardiorespiratory events (apnea/ bradycardia/desaturation) relative to the average frequency in the four hours prior to study initiation. For infant without any events in the four hours prior to study initiation, greater than one event per hour will be used as a threshold. Further, any single event requiring bag- mask positive pressure ventilation will lead to study termination.

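### The in-session heart-rate stop covers only a rise, so one sustained fall need not end the session if events are counted per hour or over the whole session

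*Combined protocol and SAP*

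**What the plan says.** All of this is in the Procedures section unless stated otherwise.

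- **Start criteria.** The session is deferred for hemodynamic instability, which for heart rate is "defined as a baseline heart rate less than 100 beats per minute (bpm) or greater than 180 bpm". This criterion is two-sided.
- **Stopping criterion (b).** The session ends for "an increase in heart rate to greater than 190 bpm" if the rise also exceeds 10% of baseline, or for a rise above 20% of baseline. Both limbs concern an increase.
- **Stopping criterion (d).** Apnea, bradycardia and desaturation are counted together. The session stops when their hourly frequency doubles against the average of the previous four hours. For an infant with no events in those four hours, "greater than one event per hour will be used as a threshold". One event alone stops the session only if it needs bag-mask ventilation.
- **Other stops.** Criterion (a) covers a drop in mean arterial pressure. Criterion (c) covers SpO2 in tiers that shorten with depth: a drop "to less than 80% for greater than one minute", below 75% for more than 30 seconds, or below 45% for any time.
- **Stated intent.** "These criteria are designed to be conservative safety measures".
- **Timing.** "V/Q will first be measured on two separate occasions 30 minutes apart at baseline CPAP"; after each CPAP change, "A period of 15 minutes will elapse to allow equilibration of lung volumes"; and "The study protocol will typically require between 60 and 120 minutes".

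**The concern.** The plan regards a heart rate below 100 bpm as a reason not to start, yet no heart-rate limit ends the session if the rate falls below 100 bpm once it is under way. A fall can act only through the event count in (d), and that count measures how often events occur, not how long one lasts. A single long bradycardia could therefore carry the same weight as a single brief one.

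Followed literally, the rules would then allow the session to continue during a sustained low heart rate, with another pressure step if V/Q had improved, because further steps depend on V/Q and not on heart rate. The plan itself names adverse cardiopulmonary interaction as a plausible harm of excess pressure (Secondary outcome variable(s)). It adds that modern CPAP level studies have not observed it.

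**Working it through.** The plan gives no calculated figure to reproduce here. The check applies the written rules to one case: a sustained fall counted as one event, with no bag-mask ventilation and no breach of the SpO2 or mean pressure limits.

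**1. No events in the previous four hours; limit more than 1.0 per hour.** Rate = 60 / window in minutes.

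| Counting window | Rate per hour | Stop under (d)? |
|---|---|---|
| Any one hour | 60/60 = 1.0 | No |
| Whole session, 60 min | 60/60 = 1.0 | No |
| Whole session, 90 min | 60/90 = 0.67 | No |
| Whole session, 120 min | 60/120 = 0.5 | No |
| One CPAP level, 24 min | 60/24 = 2.5 | Yes |

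The 24 minutes is the plan's minimum: 15 min equilibration plus one V/Q measurement of 3 pairs × (1 min stabilization + 2 min recording) = 9 min, with no time allowed for FiO2 titration.

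**2. Running rate from the start of the first baseline.** At minute t the rate is 60/t, so one event stops the session before minute 60 and not from minute 60 on. Taking the two baseline measurements as starting 30 minutes apart:

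- The second baseline ends at 30 + 9 = 39.
- The +1 level runs from 39 to 39 + 24 = 63.
- The +2 level starts at 63 and the +3 level at 63 + 24 = 87.
- After a non-response and 15 min back at baseline, the −1 level starts at 63 + 15 = 78 and the −2 level at 78 + 24 = 102.

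One event at +2, +3, −1 or −2 gives at most 60/63 = 0.95 per hour, so no stop. An event during the baselines, or in the +1 step before minute 60, does stop the session. If the four SpO2 readings fall at 0, 30, 60 and 90 seconds, a pair takes 2.5 min and a measurement 7.5 min. The +2 level then starts at 30 + 7.5 + 15 + 7.5 = 60, where the rate is 1.0 and still not above the limit.

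**3. Infants with prior events, whole-session counting.** Threshold = 2 × (prior events / 4), read as met when the rate reaches it.

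| Prior events in 4 h | Threshold per hour | One event in 60 / 90 / 120 min (1.0 / 0.67 / 0.5) |
|---|---|---|
| 1 | 0.5 | Stops at all three |
| 2 | 1.0 | Stops at 60 min only |
| 3 | 1.5 | Does not stop |

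With more than three prior events the threshold is higher still. The start criteria allow up to six stimulated events in six hours, so such infants are eligible.

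**4. Asymmetry of (b).** A rise stops the session above the smaller of 1.2 × baseline and max(190, 1.1 × baseline): above 120 bpm at baseline 100, 180 at baseline 150, and 198 at baseline 180. No size of fall stops it under (b).

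**5. Infants still to be studied.** The status section gives 12 enrolled at Penn and 15 at participating centers; the Modification Summary gives 4 who did not reach the intervention and a target of 20 treated. Treated so far is at most 12 − 4 = 8 or 15 − 4 = 11, so at least 20 − 11 = 9 or 20 − 8 = 12 remain. This assumes that the two counts overlap. Added together they would give 27 − 4 = 23 treated, already above the target.

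**The case against.** The strongest reply is that bradycardia is not overlooked: the plan puts rises in (b) and falls in (d), and ends the session for any event needing bag-mask ventilation. That is correct. A reader might infer that the plan ignores a low heart rate, and the documents do not support it. Counting brief bradycardias in (d) is a reasonable choice.

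A second reply is that (d) sets no window. CPAP level is a natural one, since heart rate and blood pressure are recorded at the end of each level, and a single event would then stop an infant with no prior events. This also stands. It rules out the stronger reading that a sustained fall can never stop such a session. What remains is that the outcome depends on a window the text does not fix.

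Third, the scenario needs several conditions together, and safeguards exist. A team member stays at the bedside, the units have cardio-respiratory monitors, the SpO2, pressure and bag-mask stops apply, and a committee with two neonatologists not directly involved reviews safety after 7 and 14 subjects. Stopping rules are also minimum triggers, so it would be wrong to read them as telling staff to continue. All of this lowers the risk, but none of it is a written lower heart-rate stop. Mean pressure is scheduled for recording only at the end of each period, usually by cuff. The committee reviews after the fact.

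Finally, a floor of 100 bpm would leave a fall from 180 to 101 bpm (79/180 = 43.9%) untouched. That is true. However, a 20% relative limit would stop that infant below 0.8 × 180 = 144 bpm, well inside the range the plan accepts at the start. The 100 bpm floor follows the plan's own definition of instability.

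**Conclusion.** The point holds as a limited gap. Criterion (b) is one-sided where the start criterion is two-sided, and (d) does not reliably close the difference. With no events in the previous four hours, one sustained fall need not stop the session under per-hour counting (1.0) or whole-session counting (0.5 to 1.0), against a limit of more than 1. Under whole-session counting the same holds with three or more prior events, or with two in sessions longer than 60 minutes. Under per-level counting (2.5 per hour), an infant with no prior events would be stopped.

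This rests on counting one sustained fall as one event, which is the natural reading but is not stated, and on none of the other stops being met. A reader might infer that infants are being exposed to frequent unrecognized bradycardia. The documents give no frequency, and the event is probably uncommon. The change is a modest safety improvement, worth making for the infants still to be studied.

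**What to change.** For infants not yet studied, add to criterion (b):

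> or, with an adequate pulse waveform, a fall in heart rate to below 100 bpm and more than 10% below baseline for more than one minute, or to below 80 bpm for more than 30 seconds.

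The 100 bpm comes from the start criterion, the 10% from (a) and (b), and the waveform condition and two durations from (c). The 80 bpm is an assumption, 20% below the 100 bpm floor (0.8 × 100). The clinical lead should confirm it as one fixed number before the IRB modification, and no duration should be left open in the text.

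The first tier acts below the smaller of 100 bpm and 0.9 × baseline: below 90 at baseline 100, below 99 at 110, and below 100 at 112 or higher. The second tier keeps a deeper fall from having to last a full minute.

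Leave (d) unchanged so that brief bradycardias still count. Include stops under the new limb in the termination proportion reported under Data and Safety Monitoring.

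The cost is one clause and an IRB modification. No equipment is needed, because the study oximeter already displays heart rate. There may be a few more early terminations, and these count toward the plan's expectation of less than 20%.
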